## Introduction

Colorectal cancer is the third most commonly diagnosed cancer in the world. It accounts for 11% of all cancer diagnoses, and is the fourth leading cause of cancer mortality, with 1.8 million new cases and approximately 861,000 deaths in 2018 (GLOBOCAN CHI database). Surgical resection is the mainstay of therapy for patients with non-metastatic disease, and has a significant impact on the long-term survival of patients with metastatic disease (3). Outcome is closely related to the quality of preoperative staging, surgery, and multidisciplinary patient management (4-5).

Anastomotic dehiscence (AD) is the most feared complication following resective colorectal surgery due to the high rate of morbidity and mortality that results from the worsening of the overall and oncological outcome of the patient and the increase in the time and costs of hospitalization (6). The International Study Group of Rectal Cancer has defined AD as “a communication between intra and extra luminal compartments due to a defect in the integrity of the intestinal wall at the anastomosis between intestinal segments” (7). In literature the mortality rate resulting from AD is very variable.

An Australian study of 1,598 patients recorded a mortality rate of 1.7% (8), but other case studies report a higher percentage, up to 29%. (9-10-11). Approximately 1/3 of deaths following colorectal surgery are attributable to this complication (12).

The incidence varies depending on the anatomical location of the anastomosis: 1--20% in the case of colorectal anastomosis; 0--2% in the case of colo--colic anastomosis and 0.02--4% in the case of ileo--colic anastomosis (13--14--15--16). Risk factors for anastomotic leakage can be divided into preoperative, intraoperative, and postoperative factors.

All can be traced back to two main groups: local, related to the surgical technique, and general, related to the patient. As regards local factors, the most significant are: experience of the surgeon (especially in the case of laparoscopic surgery), distance from the anal margin, suturing of the anastomosis using manual or mechanical staples, type of anastomosis (lateral--to--side, end--to--side, end--to--end), tension, vascularization and hemostasis of the anastomotic ends, presence of a

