protective stoma, placement of drains, bowel preparation, role of the microbiome (17). Review from 2015 identified several patient-related modifiable and non-modifiable risk factors, including: male sex, smoking, habits, alcohol consumption, obesity, diabetes, vascular disease, use of anti-inflammatory drugs, transfusions, hypoalbuminemia, anemia, intraoperative hypotension and use of cardio-vascular drugs, neoadjuvant radiotherapy and chemotherapy(18).

A factor that occurs in almost all these conditions is an alteration in tissue perfusion, and therefore in oxygen availability with consequent micro-ischemia of affected segments and failure of the anastomosis.

Reduced availability of oxygen, in addition to the patient's condition, which can affect it both pre- and post-operatively, can also occur intraoperatively. Good tissue oxygenation can favorably influence the outcome of anastomoses. One study in fact has documented a reduction in the risk of AD following colorectal and gastric surgery with the administration of supplemental oxygen alone (FiO2 80%) during the procedure and for 6 hours thereafter (19).

However, the availability of O2 is not determined exclusively by the inspiratory fraction of O2, but by factors present in the equation that defines the Oxygen Availability (DO2):

$$DO_2 = CO \times CaO_2, \text{ where } CaO_2 = (Hb \times SaO_2 \times 1,39) + (0,0031 \times PaO_2)$$

CO: Cardiac Output; CaO2: Arterial Oxygen content

In this equation the portion of DO2 attributable to the dissolved form of O2 in arterial blood (PaO2) is negligible. Therefore the following equation can be considered:

$$DO_2 = CO \times Hb \times SaO_2 \times 1,39$$

Considering all the parameters involved allows to have a more correct and complete idea of peripheral tissue perfusion. There is only one study in literature in which the indexed DO2 (DO2I) is put in relation to the incidence of AD (20). In this study the CO of 75 patients undergoing colonic

resection was monitored via Doppler probe in the esophagus. The results show that patients with a DO2I <400 ml/min/m^2 have a significantly higher risk of developing AD.

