The use of the esophageal Doppler probe for monitoring cardiac dynamics is, however, highly invasive and cannot ignore the operator's experience. Furthermore, it requires frequent checks of the correct positioning of the probe itself. It also presents some, albeit rare, contraindications. Currently, there are several methods for cardiovascular monitoring that allow obtaining sufficiently reliable hemodynamic data while being less or absent invasive and easy to interpret. Through non-invasive analysis of the shape of peripheral blood waveform (pulse--contouring volume--clamp technique) by inflating a cuff placed on the patient's finger, it is possible to obtain complete information about volume status and preload, cardiac function and afterload, in an easily usable format (21--22).

To calculate DO2I it is also necessary to know the patient's total hemoglobin (Hb) value, data obtainable with a blood test, normally performed preoperatively. However, during the surgical intervention, numerous factors contribute to modifying the Hb concentration, such as the patient's volume status and blood loss.

To obtain reliable intraoperative data, it would therefore be necessary to resort to serial blood sampling, venous or arterial which is clearly invasive for the patient and an expenditure of economic resources. Currently, there are new-generation pulse oximeters on the market that analyze different wavelengths and simultaneously measure multiple parameters: O2 saturation, heart rate, respiratory rate, total hemoglobin, carboxyhemoglobin, and methemoglobin, arterial O2 content, perfusion index, and plethysmographic variability index.

With this new technology it is therefore possible to obtain non-invasively and continuously more real and complete data, little influenced by patient movement and by conditions of low perfusion (23--24).

Aim of the study

To evaluate the effects of DO2I on the incidence of AD in patients undergoing laparoscopic resection for colorectal cancer.

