## Materials and Methods

Patients attending the General Surgery Unit of the S. Eugenio Hospital in Rome will be enrolled who meet the following inclusion criteria:

- age > 18 years

- candidates for laparoscopic colorectal surgery in elective for neoplastic pathology

Patients will be excluded if they meet the following criteria:

- age < 18 years

- inability to express valid informed consent

- interventions that involve other areas of the body in addition to the colon and rectum

- emergency interventions

- open surgical interventions

- patients who have contraindications to the use of the volume--clamp system for hemodynamic monitoring (conditions that alter significantly the perfusion of the fingers, e.g. Raynaud's disease)

Each patient will follow a preoperative evaluation according to the clinical standards of the Anesthesia and Intensive Care Unit of the two recruiting centers: a complete physical examination will be conducted for all areas and a medical history aimed at identifying general and specific risk factors, and assigning a risk class of the American Society of Anesthesiologists (ASA).

During the preoperative period a blood sample will be taken for a complete blood count coagulation tests, and chemistry tests.

All patients will be given a dedicated informed consent form which will explain the aims and methods of the study. Furthermore, all patients will be informed that the anesthesiological care is of equal intensity in each case, in accordance with the dictates of common and good clinical practice.

Patients will be subjected to general anesthesia (GA) with titrated doses of propofol 1%, fentanyl, rocuronium, desflurane, oxygen, and air, with complete noninvasive monitoring.

All enrolled patients will also be provided with non-invasive hemodynamic monitoring for the calculation of CO based on pulse-contouring type volume clamp, via the ClearSight system (Edwards Lifescience Corporation--USA). Non-invasive monitoring will also be applied for oxygen calculation using pulse oximetry sensors Masimo rainbow (Masimo Corporation – Irvine, California). The DO2I will be calculated at three moments and periods during the procedure: 5 minutes after the induction of GA, 30 minutes after the induction of pneumoperitoneum, 5 minutes after the end of pneumoperitoneum. This is intended to record the variation in DO2I in relation to the hemodynamic changes induced by pneumoperitoneum.

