All patients enrolled will constitute Group A. Based on the average of three measurements of DO2I obtained during the intervention, patients in Group A will be distributed into three subgroups: DO2I <400 ml/min/m^2 (Group A1), DO2I 400--600 ml/min/m^2 (Group A2), DO2I >600 ml/min/m^2 (Group A3). The values of DO2I chosen as cut-offs for the formation of the three subgroups were established by analyzing the studies by Levy and by Shoemaker (20--25). For each of the three subgroups the incidence of AD will be calculated, also in relation to anamnestic risk factors.

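### Nothing in the plan keeps the intraoperative DO2I values from those who suspect, work up or code anastomotic dehiscence, so detection that depends on exposure is possible

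*Combined protocol and SAP*

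**What the plan says.** The stated aim is to evaluate the effect of DO2I "on the incidence of AD in patients undergoing laparoscopic resection for colorectal cancer".

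Materials and Methods sets out the exposure. "All enrolled patients will also be provided with non-invasive hemodynamic monitoring for the calculation of CO", and pulse oximetry sensors supply the oxygen variables. DO2I "will be calculated at three moments and periods during the procedure": shortly after induction of anaesthesia, half an hour into pneumoperitoneum, and shortly after pneumoperitoneum ends. From the average of the three readings "obtained during the intervention, patients in Group A will be distributed into three subgroups": A1 below 400, A2 from 400 to 600, A3 above 600 ml/min/m2.

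The outcome follows in the same section: "For each of the three subgroups the incidence of AD will be calculated, also in relation to anamnestic risk factors". Statistical Analysis assigns Fisher's exact test to categorical variables, with significance at p < 0.05.

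Two statements in the Introduction bear on the point. It quotes a published definition of AD, "a communication between intra and extra luminal compartments due to a defect in the integrity of the intestinal wall at the anastomosis", which the Methods do not take up as the endpoint definition. It also reports from one earlier study that patients below 400 ml/min/m2 "have a significantly higher risk of developing AD".

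**The concern.** AD after surgery is found because someone suspects it and looks for it. Here the exposure data exist before that happens, the protocol itself reports that low values go with more AD, and the same 400 ml/min/m2 threshold defines A1. If a clinician who knows of a low DO2I investigates more readily, or if a coder who knows it classifies a doubtful case as AD more readily, A1 will show more AD than A3 even where the true risk is the same.

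This error would not be random: it would push the result towards the hypothesis on the study's only question. Fisher's exact test cannot reveal it, because the probability of detection in each subgroup is never recorded, and a larger sample does not shrink it.

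**Working it through.** **Sequence in the text**

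1. DO2I is calculated at three points in the operation, the last one after pneumoperitoneum ends (Materials and Methods). The data that determine A1, A2 or A3 are therefore complete by the end of surgery.
2. The text does not say when the average is taken or the label assigned. In the sentence on grouping, the words about the intervention describe the measurements, not the allocation to subgroups.
3. The text does not say who calculates DO2I, who sees it, or whether it reaches the ward.
4. Materials and Methods and Statistical Analysis contain no concealment of readings, no AD assessor unaware of DO2I, no uniform work-up and no time window for AD.

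So a path from exposure to detection is open. The text does not show that it will be taken.

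**Size, as illustration only**

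The plan gives no sample size, event count or detection probability, so there is no figure of its own to reproduce. Assume the same true AD risk p in two groups, no false-positive diagnoses, and detection probabilities s1 (low DO2I) and s2 (others).

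Apparent risk ratio = (p × s1) / (p × s2) = s1 / s2

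- 0.90 / 0.85 = 1.06
- 0.95 / 0.80 = 1.19
- 1.00 / 0.70 = 1.43
- 0.95 / 0.60 = 1.58

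The true risk p cancels, and so does the sample size.

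The next table shows how often a two-sided Fisher test at 0.05 would be significant with no true difference, by exact enumeration for two equal groups. Group sizes and detection probabilities are assumptions. The true rates of 10% and 20% lie within the 1–20% that the Introduction gives for colorectal anastomosis.

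| True AD rate | Detection s1 vs s2 | n = 50 per group | n = 100 | n = 200 |
|---|---|---|---|---|
| 10% | 0.90 vs 0.90 | 1.6% | 2.8% | 3.3% |
| 10% | 0.95 vs 0.80 | 2.0% | 3.9% | 5.8% |
| 10% | 0.95 vs 0.60 | 3.6% | 9.8% | 20.1% |
| 20% | 0.90 vs 0.90 | 2.7% | 3.3% | 3.6% |
| 20% | 0.95 vs 0.80 | 3.8% | 6.1% | 9.8% |
| 20% | 0.95 vs 0.60 | 9.9% | 22.2% | 43.7% |

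At a true rate of 2% the figure stays below 3% in every scenario. A moderate detection gap therefore distorts the estimate more than it inflates the test; strong inflation needs a wide gap, a common outcome and a large sample.

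**The case against.** A reader might infer that the subgroup is fixed in theatre by a team that sees the readings, and that the surgeons who later diagnose AD know each patient's group. The documents do not support this. They time the measurements, not the labelling. The remark in the Introduction that finger-cuff monitoring yields "complete information about volume status and preload, cardiac function and afterload, in an easily usable format" describes the technology in general; it does not mention DO2I or say that the surgeons receive it. DO2I has to be computed by combining cardiac output from one system with haemoglobin and saturation from another, and no section says that either device displays it.

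A reader might also infer that such bias could never be examined afterwards. That goes too far: masked review of records, or an analysis restricted to overt or re-operated leaks, could at least probe it.

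It is also fair to say that the size rests wholly on assumptions, and that in the middle case (0.95 against 0.80) the test stays between 2.0% and 5.8% at a true rate of 10%, close to or below the nominal level.

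Finally, if surgeons in theatre do see the values, a separate sheet does not blind them, and they may be the people who decide on re-operation. That objection stands, and it limits what the fix can achieve.

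None of this closes the gap: the plan contains no step that separates the assessment of AD from knowledge of DO2I. The observational design does not answer the point either, since AD must still be detected and coded by someone.

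**Conclusion.** The point holds as a possibility that the plan leaves open, not as a demonstrated bias. The determining data precede the diagnosis of AD, the protocol names the expected direction, and nothing keeps DO2I from those who suspect, work up or code AD. Any resulting bias would probably favour more AD in A1.

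Its size is unknown. Risk ratios of 1.06 to 1.43, or 1.58 for a wider gap, hold only under the assumed detection probabilities, equal true risk and no false-positive diagnoses. The change is worth making because it is cheap and has to be in place before AD is coded.

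**What to change.** In the part of Materials and Methods that forms the subgroups, set this order:

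1. The calculated DO2I values go on a research sheet held by the anaesthesia team.
2. For every patient, AD status is coded by an existing member of the surgical team who has not seen the DO2I values, using the AD definition already quoted in the Introduction.
3. AD status is locked.
4. Only then is the mean DO2I calculated, A1/A2/A3 assigned, and the result merged with AD.

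The cost is a few sentences and one data sheet, with no extra staff, procedures or patients. The coder does have to be chosen from those who have not seen the values.

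The downsides are that subgroup results wait for the AD lock, and that theatre staff who see the monitors remain unblinded. The step protects coding best and clinical suspicion only in part; the report should state this as a limitation. It also does not supply the uniform work-up and time window that the Methods lack; the investigators should state these separately.

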## **Statistical Analysis**

The data will be analyzed using the IBM SPSS software package (Armonk, NY), with calculation of medians and standard errors. For continuous variables, the t-test and ANOVA will be used. For categorical variables, the Fisher's exact test will be used. A p value < 0.05 will be considered statistically significant.

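### AD is compared across observed DO2I subgroups with an unadjusted test only, and anastomotic site, which the plan itself says changes AD incidence, is left out

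*Combined protocol and SAP*

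**What the plan says.** The aim is worded as a question about effect: "To evaluate the effects of DO2I on the incidence of AD" (Aim of the study). Under Materials and Methods, patients are placed in A1 (below 400 ml/min/m²), A2 (400 to 600) or A3 (above 600) by the mean of three intraoperative measurements. Nothing is randomised. The planned analysis of AD is: "For each of the three subgroups the incidence of AD will be calculated, also in relation to anamnestic risk factors". No factor is named and no method is given.

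Statistical Analysis names the t-test and ANOVA for continuous variables. For a binary outcome such as AD it says: "For categorical variables, the Fisher's exact test will be used". No regression, stratified test or other adjustment appears.

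On site, the Introduction says: "The incidence varies depending on the anatomical location of the anastomosis". It gives 1–20% for colorectal, 0–2% for colo-colic and 0.02–4% for ileo-colic anastomoses. On risk factors it says: "All can be traced back to two main groups: local, related to the surgical technique, and general, related to the patient". The local list includes "distance from the anal margin, suturing of the anastomosis using manual or mechanical staples, type of anastomosis". Eligibility covers "candidates for laparoscopic colorectal surgery in elective for neoplastic pathology", with no restriction or stratification by site.

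**The concern.** Because the subgroups come from an observed value, nothing in the design balances other causes of AD across them. The plan identifies one such cause, anastomotic site, and then leaves it out of the comparison. The phrase about anamnestic factors does not plainly fill the gap: it refers to patient history, whereas the Introduction classes distance from the anal margin and type of anastomosis as local, surgical factors.

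If A1 held more colorectal anastomoses than A3, A1 would show more AD even if DO2I had no influence. If A3 held more, a real effect would be understated. Without a within-site table or a site-adjusted estimate, a reader of the results could not tell which of these had happened, or whether neither had.

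**Working it through.** The plan states no sample size, power, effect size or site mix, so there is no figure of its own to reproduce. Every input below is an assumption unless marked as from the documents.

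**1. Bias in the crude risk ratio, no DO2I effect.** Assume AD of 10% at colorectal and 2% at other anastomoses; both lie inside the Introduction's ranges. With colorectal share c, crude AD = 0.10c + 0.02(1 − c) = 0.02 + 0.08c.

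| Colorectal share, A1 vs A3 | Crude AD | Crude RR | Reversed |
|---|---|---|---|
| 70% vs 50% | 0.076 vs 0.060 | 1.27 | 0.79 |
| 65% vs 55% | 0.072 vs 0.064 | 1.125 | 0.89 |

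Range over the Introduction's own rates at 70% vs 50%:
- 20% vs 0%: 0.140/0.100 = 1.40
- equal rates at all sites: 1.00
- 1% colorectal vs 4% other: 0.019/0.025 = 0.76

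A true RR of 2 would read 2 × 0.076/0.060 = 2.53, or 2 × 0.060/0.076 = 1.58.

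**2. Comparison with sampling error.** Assume N = 300 and DO2I ~ Normal(500, 120). Then P(DO2I < 400) = Φ(−0.833) = 0.202, and the same share lies above 600, so A1 and A3 hold about 61 patients each. Expected events are about 4.6 and 3.6. SE(log RR) ≈ √(1/4.6 + 1/3.6 − 2/61) ≈ 0.68, against ln 1.27 = 0.24. The shift is about a third of one standard error.

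**3. Rejection rates.** These come from simulation with 4,000 replicates per setting (Monte Carlo SE at most 0.8 points), α = 0.05 and the site rates above. The crude test is the exact 3×2 Fisher test. The stratified test is the 2-df Mantel-Haenszel test of general association over two sites. The assumed effect is an odds ratio of 0.6 per +100 ml/min/m². This is large: by integration over the DO2I distribution it gives AD of 14.6% in A1 and 3.2% in A3 at equal site mix, an RR of about 4.6.

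| Colorectal share A1/A2/A3 | N=300 crude / stratified | N=150 | N=75 |
|---|---|---|---|
| 60/60/60 | 52% / 54% | 27% / 28% | 13% / 15% |
| 50/60/70 | 39% / 54% | 19% / 30% | 11% / 17% |
| 70/60/50 | 68% / 54% | 38% / 28% | 18% / 16% |

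The 68% is not a gain in power; part of it is confounding. N = 75 is included because it is the size of the one earlier study described ("In this study the CO of 75 patients undergoing colonic").

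With no DO2I effect, crude rejection is 3.6–5.3% and stratified rejection 4.1–4.8% in these mixes. If site is irrelevant (3% everywhere, N = 300), the two tests reject 29% and 28–29% of the time, so stratifying costs nothing material.

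**4. Events available.** At a 60% colorectal share and no DO2I effect, overall AD = 0.02 + 0.08 × 0.6 = 0.068. Expected events are 20.4, 10.2 and 5.1 at N = 300, 150 and 75. At N = 75 the non-colorectal stratum has 30 patients, and the chance of no AD in it is 0.98³⁰ ≈ 0.55.

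**The case against.** The strongest objection is that the confounding is assumed. Nothing in the documents links anastomotic site to DO2I, and with equal site mix the crude and stratified tests hardly differ (52% vs 54%). This stands, and it limits the point to a risk of unknown direction and size.

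The swing from 39% to 68% also needs an assumed N of 300 and an effect equivalent to an RR of about 4.6. At N = 75 both tests have little power whatever the mix. That stands too.

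A reader might infer that the planned test would produce a false DO2I finding. The documents do not support this. At 70% vs 50% the false-positive rate stays near 5%. Material inflation needs more extreme assumptions. For example, with colorectal shares of 70% vs 30%, the midpoints of the published ranges and two equal subgroups, Fisher's test rejects 10.4% of the time at 100 per subgroup and 22.6% at 200. No such imbalance is documented.

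It can also be said that the plan does intend to look at risk factors, since the preoperative history is meant to identify general and specific ones. This is a partial answer: no factor list or method follows, and site is an operative fact.

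Finally, site may not be the most important confounder. The Introduction ties almost all the listed risk factors to altered perfusion and oxygen availability, and haemoglobin and cardiac output are terms in its DO2 equation. This stands. Stratifying by site does not control those factors, and the result must not be presented as if it did.

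**Conclusion.** The gap is real but conditional. Observed subgroups are compared with an unadjusted test, while a determinant of AD that the plan itself names has no place in the analysis. If site mix differs between subgroups, the crude comparison is biased. Under the assumed rates and a 20-point difference in colorectal share, the crude risk ratio is multiplied by 1.27 or 0.79. That is modest beside the sampling error, and it does not push false positives much above 5%. The effect on rejection becomes large only with a large assumed effect and N around 300. If site mix is equal, little is gained.

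It would go too far to say that the planned comparison is biased in a known direction, or that adjusting for site would make the result causal. The documents support neither. This is a cheap improvement of lower severity.

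**What to change.** Record anastomotic site (colorectal vs colo-colic or ileo-colic) from the operative record, and add to Statistical Analysis:

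> The main comparison of AD across A1, A2 and A3 is a Mantel-Haenszel test of general association stratified by anastomotic site. It is reported with site-adjusted Mantel-Haenszel odds ratios or risk ratios and 95% confidence intervals for A1 vs A3 and A2 vs A3. AD by DO2I subgroup is tabulated within site. The crude Fisher's exact test is secondary. Results are reported as associations: most known risk factors for AD are themselves related to perfusion and oxygen availability, and stratification by site does not control these patient-related factors.

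The adjusted ratios matter as much as the test, since the harm is a biased estimate and a p-value alone would not correct it.

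The cost is one variable and a few lines of text, with no new procedure. The main drawback is sparse data: at small N the non-colorectal stratum may contain no AD and then adds nothing to the test, so the adjusted estimates may be imprecise. If the stated software does not run the stratified test for three groups, the plan should name a package that does.
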